Carnitine Supplementation and Skeletal Muscle Function

22/06/2015

OBJECTIVE: To evaluate the effect of carnitine supplementation as the anti-inflammatory intervention for exploring the relationship between inflammation and associated with aging reduction of skeletal muscle mass;

DESIGN: Male and female volunteers over 60 years old are recruited to participate in the study (n=40). Subjects with diabetes, liver, or renal diseases and gastro-intestinal illnesses as well as all using vitamin supplements are excluded from the study group. The patients are randomly assigned to two experimental groups (n=20). All patients are subjected to consume gelatin capsules every day throughout the study. During the 24-weeks intervention period, Group A undergoes carnitine (1.5g) supplementation, whilst group B undergoes a placebo supplementation. Measurements are performed before, at the mid-point, and at the end of the intervention period (see primary and secondary output variables below).

METHODS:

- Plasma cytokines concentration Plasma cytokines (TNF-α, IL-1 and IL-6) as well as CRP is determined by enzyme immunoassay methods using high sensitivity commercial kits.
- *Biodex* The maximal isometric knee extensor peak torques is determined for all subjects by using a dynamometer to evaluate the relative changes in maximal force-generating capacity over the time course of supplementation. All subjects is familiarized with the testing protocol at least 2 weeks before testing baseline muscle strength measurements. To standardize the testing, subjects will have their shoulders strapped to the chair with adjustments for the back and hips and will perform each protocol in the sitting position. Each subject will perform three repetitions for the isometric contraction, with 90 s of rest between the repetitions (the subject's knee at an angle of 70°). The highest peak torque value is considered as the maximal value after recording for all repetitions.
- Octapolar bioimpedance analysis of body composition Each participant is weighted in accordance with the manufacturer's guidelines of the multifrequency analyzer. The contact with a total of 8 electrodes (2 for each foot and hand) gives the body composition analysis: dry lean mass, lean body mass, body fat mass, percent body fat and segmental lean analysis
- Plasma FFA and glycerol Plasma samples is taken in fasted state before starting and after finishing the training protocol. FFA and glycerol concentrations is determined by routine enzymatic spectrophotometric assays in the laboratory of prof. [name].
- Global Physical Activity Questionnaire Developed by WHO questionnaire for physical activity surveillance. It collects information on physical activity participation in three domains: activity at work, travel to and from places and recreational activities; as well as sedentary behaviour, comprising 16 questions.

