Carnitine Supplementation and Skeletal Muscle Function

NCT02692235

28/02/2017

Basic anthropometric characteristics of the subjects were evaluated as mean \pm SD. For educational and physical activity levels, a percentage of the total tested was used, while a frequency of meat consumption was presented as median and range. Changes in both groups across the supplementation time and ratios as well as changes in other measurements were analyzed with a Microsoft Excel (Microsoft Office) spreadsheet for the analysis of parallel-group controlled trials. For this, effects were interpreted using magnitude-based inferences. All data were log-transformed for analysis to reduce bias arising from non-uniformity of error; means of change scores in the placebo and l-carnitine groups, standard deviations of change scores, and effects (variations of change in both the means and their confidence limits (CL)) were back-transformed to percent units. Mean changes and effects were adjusted to the overall mean baseline value of the placebo and l-carnitine groups, by including the baseline value as a covariate in the analysis. Magnitudes of the effects were evaluated with the log-transformed data by standardizing the deviation of the baseline values of the placebo and l-carnitine groups. Threshold values for assessing magnitudes of standardized effects were 0.20, 0.60, 1.2 and 2.0 for small, moderate, large and very large respectively. Uncertainty in the effects was expressed as 90% CL and as probabilities that the true value of the effect was beneficial, trivial or harmful. These probabilities are not presented quantitatively but were used to make qualitative probabilistic clinical inferences about effects in preference to a statistical inference based on a null-hypothesis significance test. The effect was deemed unclear when the chance of benefit was sufficiently high to warrant the use of the treatment but the risk of harm was unacceptable. Such unclear effects were identified as those with an odds ratio of benefit to harm of <66 , a ratio that corresponds to an effect that is borderline possibly beneficial (25% chance of benefit) and borderline most unlikely harmful (0.5% risk of harm). All other effects were deemed clinically clear and the likelihood of the true effect as being trivial, beneficial or harmful was expressed with the following scale: 25–75%, possibly; 75–95%, likely; 95–99.5%, very likely; $>99.5\%$, most likely. To maintain an overall error rate of $<5\%$ to declare one or more changes as having opposite magnitudes (a substantial decrease instead of an increase, and vice versa), the effects were also evaluated as beneficial or harmful with a threshold of 1%, equivalent to the consideration of the overlap of substantial values with a 98% confidence interval (CI).

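### Does timing the FFA and glycerol samples by a training protocol that is never described leave the sampling schedule unusable?

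*Protocol*

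**What the plan says.** The protocol's DESIGN section describes one intervention: "During the 24-weeks intervention period, Group A undergoes carnitine (1.5g) supplementation, whilst group B undergoes a placebo supplementation". It then gives a general schedule: "Measurements are performed before, at the mid-point, and at the end of the intervention period". That sentence exempts no variable, but it points forward to the outcome variables for detail.

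Under METHODS, the plasma FFA and glycerol item has its own timing: "Plasma samples is taken in fasted state before starting and after finishing the training protocol". No other METHODS item states blood-draw times. The cytokine item, for example, gives only the assay method.

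The nearest similar phrase is in the Biodex item on knee-extensor strength: "All subjects is familiarized with the testing protocol at least 2 weeks before testing baseline muscle strength measurements". That item goes on: "Each subject will perform three repetitions for the isometric contraction, with 90 s of rest between the repetitions".

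The SAP names neither FFA nor glycerol, and it lists no visits. It says: "Changes in both groups across the supplementation time and ratios as well as changes in other measurements were analyzed". The analysis uses log-transformed change scores, compared between the two groups with the baseline value as a covariate.

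**The concern.** Two things look wrong.

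- **The anchor is undefined.** The word *training* appears once in the two documents, in the sentence that tells staff when to draw these samples. Read literally, the draws are tied to an event that the protocol does not contain.
- **The number of draws differs.** The item gives two times where the general schedule gives three, and it does not say that this is an exception.

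At stake is what the FFA and glycerol results would measure. If *training* stands for supplementation, they measure a 24-week change. If it stands for the strength-testing procedure, they measure an acute response around a short isometric test, which says little about six months of carnitine. If sites followed different readings, the two quantities would be mixed. It would also be unclear whether a mid-point value should exist.

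**Working it through.** There is no stated figure to reproduce. The check is a comparison of the texts and a count of samples.

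**Which reading fits?**

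| Reading of *training protocol* | Support in the documents | Against it |
|---|---|---|
| The 24-week supplementation period | It is the only programme described, with a start and a finish. The Biodex item also frames strength as change over the course of supplementation. The SAP analyses change over supplementation time in a parallel-group comparison. | The word itself |
| The dynamometer testing procedure | The Biodex item calls it a protocol. | Nothing links blood sampling to the test, and no visit is named for such draws. |
| An exercise programme not described | The word alone | It has no trace in the objective, the DESIGN section, the other METHODS items or the SAP. |

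The first reading is clearly the best supported. The second is possible but has little behind it.

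**How far apart are the quantities?** Under the first reading the paired samples are 24 weeks apart. Under the second they bracket a session of three contractions, which has two rests: 2 × 90 s = 180 s of rest, plus contraction time that is not given. The second quantity would not fit an analysis of change across supplementation.

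**How many samples?** Inputs: 40 participants (DESIGN), full attendance assumed.

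- Two draws, before and after supplementation: 40 × 2 = 80.
- Three draws, under the general schedule: 40 × 3 = 120.
- Difference: 120 − 80 = 40 mid-point samples. That is 40 determinations per analyte, or 40 × 2 = 80 for FFA and glycerol together, assuming single determinations.

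A larger total, 40 × 2 × 3 = 240, arises only if draws bracket the strength test *and* this is repeated at all three visits. Neither document states either condition, so that figure is hypothetical and should not be used to size the problem.

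**Does the analysis depend on the choice?** For each participant the SAP's method needs one baseline value and one later value:

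change = log(end value) − log(baseline value), compared between groups with log(baseline value) as covariate.

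Both values are available under the two-draw and the three-draw schedule. A mid-point sample enters neither term, so the 24-week contrast is the same under both. The mid-point would only add a second, intermediate contrast. Nor does the sampling sentence distinguish the groups, so the choice introduces no difference in timing between carnitine and placebo.

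**The case for a change.** The strongest case for a change is that this sentence is the protocol's only statement of when these samples are drawn, and it refers to something that is not there. Replacing one word would still not tell staff whether to draw at the mid-point, because the general schedule makes no exception. The SAP does not name the analytes and so cannot settle it. The rank of FFA and glycerol cannot be judged either, since the text available has no labelled list of primary and secondary outcomes. A corrected sentence would cost almost nothing.

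The factual part of this stands: the term is undefined, and the counts of two and three are not reconciled in writing. The step from there to a needed change does not. An item-specific schedule ordinarily takes precedence over a general one, so two draws for this item can be read as its schedule. Anyone asking for clarification would have to accept two draws as a sound answer, and that is what the item already says. Moving to three draws would add up to 80 determinations, and possibly an extra fasted draw, as a preference; it would not correct a rule shown to be wrong.

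The stated objective concerns inflammation and skeletal muscle mass and mentions neither analyte. The SAP is dated 28/02/2017, about 20 months after the protocol date of 22/06/2015, and is written in the past tense. This suggests, without proving it, that sampling was already done. If so, rewording would not alter which samples exist.

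**Conclusion.** This is a clerical slip together with an unstated exception, and analysts can fill the gap sensibly: use the fasted samples from before and after the 24 weeks, and report a mid-point value only if one was taken. The most that turns on it is whether 40 mid-point samples exist (80 against 120 in total). The 24-week comparison of carnitine with placebo for FFA and glycerol does not depend on that. The other outcomes, the sample size and the error rates are unaffected.

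The conclusion rests on two assumptions. The first is that *training* means the supplementation period, which both documents favour but neither states. The second is that no exercise component was planned and omitted from the text. If one had been, its absence from the description of the intervention would be a separate and larger matter. A brief note in the trial report of when the samples were drawn would remove the remaining doubt, but the plan does not have to change for that.

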Carnitine Supplementation and Skeletal Muscle Function

NCT02692235

28/02/2017

Basic anthropometric characteristics of the subjects were evaluated as mean \pm SD. For educational and physical activity levels, a percentage of the total tested was used, while a frequency of meat consumption was presented as median and range. Changes in both groups across the supplementation time and ratios as well as changes in other measurements were analyzed with a Microsoft Excel (Microsoft Office) spreadsheet for the analysis of parallel-group controlled trials. For this, effects were interpreted using magnitude-based inferences. All data were log-transformed for analysis to reduce bias arising from non-uniformity of error; means of change scores in the placebo and l-carnitine groups, standard deviations of change scores, and effects (variations of change in both the means and their confidence limits (CL)) were back-transformed to percent units. Mean changes and effects were adjusted to the overall mean baseline value of the placebo and l-carnitine groups, by including the baseline value as a covariate in the analysis. Magnitudes of the effects were evaluated with the log-transformed data by standardizing the deviation of the baseline values of the placebo and l-carnitine groups. Threshold values for assessing magnitudes of standardized effects were 0.20, 0.60, 1.2 and 2.0 for small, moderate, large and very large respectively. Uncertainty in the effects was expressed as 90% CL and as probabilities that the true value of the effect was beneficial, trivial or harmful. These probabilities are not presented quantitatively but were used to make qualitative probabilistic clinical inferences about effects in preference to a statistical inference based on a null-hypothesis significance test. The effect was deemed unclear when the chance of benefit was sufficiently high to warrant the use of the treatment but the risk of harm was unacceptable. Such unclear effects were identified as those with an odds ratio of benefit to harm of <66 , a ratio that corresponds to an effect that is borderline possibly beneficial (25% chance of benefit) and borderline most unlikely harmful (0.5% risk of harm). All other effects were deemed clinically clear and the likelihood of the true effect as being trivial, beneficial or harmful was expressed with the following scale: 25–75%, possibly; 75–95%, likely; 95–99.5%, very likely; $>99.5\%$, most likely. To maintain an overall error rate of $<5\%$ to declare one or more changes as having opposite magnitudes (a substantial decrease instead of an increase, and vice versa), the effects were also evaluated as beneficial or harmful with a threshold of 1%, equivalent to the consideration of the overlap of substantial values with a 98% confidence interval (CI).

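### As written, a participant seen at the mid-point but not at week 24 cannot inform the 24-week effect; for outcomes with a mid-point, a repeated-measures model is a cheap improvement

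*SAP*

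**What the plan says.** The protocol's DESIGN section plans 20 participants per arm, followed for 24 weeks, and states: "Measurements are performed before, at the mid-point, and at the end of the intervention period".

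The SAP, a single unnumbered section, describes the analysis this way: "Changes in both groups across the supplementation time and ratios as well as changes in other measurements were analyzed with a Microsoft Excel" tool, identified as a "spreadsheet for the analysis of parallel-group controlled trials". Data are log-transformed, and the quantities carried forward are "means of change scores in the placebo and l-carnitine groups, standard deviations of change scores" and the resulting effects, back-transformed to percent. The baseline value is a covariate, so this is an analysis of covariance on change, not a comparison of raw changes.

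The SAP does not say which visits enter each analysis, how missing values are handled or who is analysed, and it specifies no model that takes the visits together. Neither document gives a dropout rate.

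One group of outcomes is described differently. For FFA and glycerol, the protocol's METHODS section says: "Plasma samples is taken in fasted state before starting and after finishing the training protocol". No mid-point sample is mentioned there.

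**The concern.** A baseline-to-week-24 change cannot be formed for a participant with no week-24 value. Under the stated method, anyone last seen at the mid-point falls out of the 24-week comparison, although the mid-point value exists and is correlated with the missing one. Nothing in the SAP shows the mid-point data informing the 24-week effect.

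Two things are at stake. Some precision is lost in a trial of 40 people. More important, if leaving the trial depends on how a participant was doing at the mid-point, and does so differently by arm, those who remain are a selected group and the arm contrast is biased. The SAP grades effects against thresholds starting at 0.20 standardised units and turns them into probabilities of benefit and harm, so a modest shift can move an effect from one category to another.

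**Working it through.** The plan has no figure on this point to reproduce: it states no dropout rate, SD or correlation.

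**Inputs from the documents.** 20 per arm; three visits; log change with baseline as covariate; smallest threshold 0.20, standardised to the baseline SD.

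**Assumed inputs.** Share f with a mid-point but no week-24 value: 10–20%. Mid-to-end correlation given baseline, ρ: 0.5–0.9. Baseline-to-end correlation r: 0.65.

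**1. Does the alternative cost anything with complete data?** Four trials were simulated with 20 per arm, unit variances and correlations 0.70 (baseline–mid), 0.65 (baseline–end) and 0.75 (mid–end). Week-24 effect, with SE in brackets:

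| Trial | Change score, baseline covariate | Repeated measures: arm × visit, baseline × visit, unstructured | Repeated measures: compound symmetry, common baseline slope |
|---|---|---|---|
| 1 | −0.026017 (0.209133) | −0.026017 (0.209133) | −0.032137 (0.202665) |
| 2 | 0.038213 (0.228583) | 0.038213 (0.228583) | 0.017275 (0.214830) |
| 3 | 0.466629 (0.176193) | 0.466629 (0.176193) | 0.451080 (0.185100) |
| 4 | 0.436037 (0.218135) | 0.436037 (0.218135) | 0.428437 (0.212234) |

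The first two columns agree to six decimals and the third does not, so the exact specification matters.

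**2. Precision with dropout after the mid-point.** Relative to full data, in large samples:

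- change-score variance = 1/(1 − f)
- repeated-measures variance = (1 − ρ²)/(1 − f) + ρ²
- ratio of the second to the first = 1 − fρ²

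For f = 0.2 and ρ = 0.7 the variances are 1.25 and 0.51/0.8 + 0.49 = 1.1275. The ratio is 0.902, so the SE falls by 1 − √0.902 = 5.0%.

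| f | ρ = 0.5 | ρ = 0.7 | ρ = 0.9 |
|---|---|---|---|
| 10% (4 of 40) | 1.3% | 2.5% | 4.1% |
| 20% (8 of 40) | 2.5% | 5.0% | 8.5% |

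(Entries are the fall in SE, 1 − √(1 − fρ²).)

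**3. Bias when 20% leave one arm in relation to the mid-point value.** Let z be the mid-point residual given baseline, in SD units. Let the dropout probability be p(z) = expit(a − s·z), with a set so that 20% drop out. Those who stay have mean z = s·E[p(1 − p)]/0.8, and the bias in the week-24 mean is ρ times that, in residual SD.

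- s = 0.5: E[p(1 − p)] = 0.154, mean z = 0.5 × 0.154/0.8 = 0.096; bias 0.048 (ρ = 0.5) to 0.087 (ρ = 0.9).
- s = 1.0: E[p(1 − p)] = 0.139, mean z = 0.139/0.8 = 0.173; bias 0.087 to 0.156.

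The range is therefore about 0.05–0.16 residual SD. The 0.20 threshold is in baseline SD, so with equal SDs at baseline and end the range is multiplied by √(1 − r²) = √(1 − 0.65²) = 0.76, giving about 0.04–0.12 baseline SD. At r = 0.9 the multiplier is 0.436 and the range is about 0.02–0.07.

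**4. Simulation check.** With 1,000 trials, the correlations in step 1 (which imply ρ = 0.54), no true effect and 20% lost from the active arm by mid-point value, analysing only those with week-24 values gave a bias of +0.055 SD (Monte Carlo SE 0.008). The repeated-measures model gave −0.003 (0.008). The data have unit variance, so these are baseline SDs. With completely random 20% dropout in both arms, neither was biased, and the empirical SDs of the estimate were 0.265 and 0.260.

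**The case against.** The strongest reply is that much of this rests on silence. A reader might infer that the SAP ignores the mid-point data. The text does not say so: changes across the supplementation time could well include a separate baseline-to-mid-point analysis. Nor do the documents show that anyone was dropped, since they give neither a dropout count nor an analysis set. What stands is narrower. The only method stated cannot use a mid-point value in the 24-week effect when the week-24 value is missing.

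A reader might also infer that the repeated-measures model can only help. That is proved for complete data alone. With dropout, the bias correction needs missing at random, and at 20 per arm the precision gain vanishes when ρ is low (SE ratio 0.999–1.002 for ρ of 0–0.2).

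The sizes are fairly called modest. The bias scenario has dropout in one arm only; the same mechanism in both arms with no true effect would largely cancel in the contrast. For scale, the sampling SE of the contrast with 20 and 16 completers is about √(1/20 + 1/16) = 0.34 residual SD, larger than any bias computed here. The model also repairs only the share ρ² of the variance lost to dropout.

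Finally, the known inefficiency of raw change scores is not an argument here, because baseline is a covariate. Change-score and final-value analyses with that covariate give the same effect and SE. All of this limits the size of the point; none of it makes the alternative costly.

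**Conclusion.** The point holds as a cheap improvement of minor severity. The stated analysis gives no weight in the 24-week effect to a participant with a mid-point but no week-24 value, and a suitably specified repeated-measures model does so without altering the complete-data result. The gain depends wholly on unstated quantities: dropout after the mid-point, the correlations between visits, and whether dropout is related to mid-point response differently by arm. If everyone completed, nothing changes.

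Two limits apply. Participants with baseline only add essentially nothing to the arm contrast under either analysis. FFA and glycerol, as described, have no mid-point value and gain nothing. Protection against bias, under missing at random, is the better reason for the change; the precision gain alone would be a weak one.

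**What to change.** For each outcome measured at the mid-point, replace the change-score analysis with one model on the log values at mid-point and end: arm by visit, baseline by visit, unstructured covariance, REML with Kenward–Roger degrees of freedom. Include all randomised participants with any post-baseline value, analysed as randomised. Report the 24-week arm contrast, back-transformed to percent. If the spreadsheet allows arm-specific variances or baseline slopes (not stated), the model should match them, so that the complete-data result stays the same.

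State which visits each analysis uses, the number with a value at each visit by arm, and the missing-at-random assumption. Keep the baseline-adjusted change analysis for FFA and glycerol, unless the three-visit statement in the protocol's DESIGN section and the two-sample description in its METHODS section are reconciled in favour of a mid-point sample.

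The cost is SAP wording, a statistical package in place of the spreadsheet, three covariance parameters per outcome and slightly more analysis work. No new data are needed.

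### Should lean-mass and torque effects be standardised by a within-sex baseline SD, because the trial recruits men and women?

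*SAP*

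**What the plan says.** The protocol (DESIGN) recruits both sexes: "Male and female volunteers over 60 years old are recruited to participate in the study (n=40", in two groups of 20. It does not give the sex split. Under METHODS, bioimpedance "gives the body composition analysis: dry lean mass, lean body mass, body fat mass, percent body fat and segmental lean analysis", and for the dynamometer "The maximal isometric knee extensor peak torques is determined for all subjects". No scaling of these measures to sex or body size is described.

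The SAP log-transforms all data, adjusts changes "by including the baseline value as a covariate in the analysis", and back-transforms effects to percent with 90% confidence limits. Magnitudes are then judged on the log scale "by standardizing the deviation of the baseline values of the placebo and l-carnitine groups". The scale is given as: "Threshold values for assessing magnitudes of standardized effects were 0.20, 0.60, 1.2 and 2.0 for small, moderate, large and very large respectively". Sex is not mentioned in the standardiser, in the covariate or among the subject characteristics that are named. The SAP does not say whether both sexes were analysed.

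Conclusions are "qualitative probabilistic clinical inferences about effects in preference to a statistical inference based on a null-hypothesis significance test". Of the chances of benefit, triviality and harm, the SAP says: "These probabilities are not presented quantitatively".

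**The concern.** Men and women can be expected to differ in lean mass and in knee extensor torque. When both are in the sample, the SD of all baseline values contains the spread within each sex and also the gap between the sexes. A limit of 0.20 such SDs is then a larger percent change than 0.20 within-sex SDs, and how much larger depends on the share of each sex.

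Three features that might seem to remove this do not:

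- Pooling the SD within treatment arms does not, because each arm would contain both sexes.
- The baseline covariate changes the effect and its error, but not the divisor.
- The log transform turns a male/female ratio into a shift, and the shift still adds variance.

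In many trials the standardiser is only descriptive. Here the verbal labels are the inference and the probabilities behind them are not shown. The same percent gain could therefore be called *likely* beneficial in one sample and *possibly* beneficial in another with a different sex mix. A result could also cross the SAP's rule for an unclear effect.

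**Working it through.** **The plan's own figure.** The unclear rule reproduces: (0.25/0.75)/(0.005/0.995) = 66.3, which matches the SAP's 66.

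**Inputs.** From the documents: 40 subjects, limit 0.20, label bands at 25, 75, 95 and 99.5%, odds-ratio cut-off 66. Assumed, because the documents do not give them: the sex difference R (in within-sex SDs of the log value), the minority-sex share p, the within-sex log SD (0.12) and the standard error (SE) of the effect (0.015 unless stated). It is also inferred that 0.20 is the limit for benefit and harm. The SAP calls it the threshold for a small effect and names no other limit.

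**Inflation of the SD.** For a mixture of two sexes, SD(all) = SD(within) × F, with F = sqrt(1 + p(1−p)R²). For example, R = 2 and p = 0.5 give sqrt(1 + 0.25 × 4) = 1.41.

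| R | F, p = 10% | F, p = 30% | F, p = 50% | F(50%)/F(10%) | F(50%)/F(30%) |
|---|---|---|---|---|---|
| 1 | 1.04 | 1.10 | 1.12 | 1.07 | 1.02 |
| 2 | 1.17 | 1.36 | 1.41 | 1.21 | 1.04 |
| 3 | 1.35 | 1.70 | 1.80 | 1.34 | 1.06 |

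Dependence on the sex mix is measured by the last two columns. The three F columns measure something else: the distance from a within-sex yardstick that the SAP did not choose.

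**Sampling noise, for scale.** With normal data, the ratio of two SDs from 40 subjects each has a 95% range of sqrt(F-quantiles with 39 and 39 df) = 0.73 to 1.38. All the mix-to-mix ratios lie inside it. The F columns can be set against the range for a single SD, sqrt(39/χ²₃₉) = 0.82 to 1.28. R = 2 at 30% or more, and all of R = 3, exceed that range. A two-sex mixture is not exactly normal, so both ranges are only a guide.

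**Effect on labels.** The log limit is 0.2 × 0.12 × F = 0.024F. The chance of benefit is 1 − T₃₇((limit − ln(1 + gain))/SE).

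- R = 2.5, gain 4%, SE 0.015: 84% (*likely*) with the within-sex SD, 73% (*possibly*) at p = 10%, 52% (*possibly*) at p = 50%.
- R = 2.5, gain 2%, SE 0.02: odds ratio 40 (*unclear*) with the within-sex SD. At p = 50% it is 72 with an 82% chance of a trivial effect (*likely trivial*).

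**How often labels move.** Share of gains, in steps of 0.1%, whose label under the mixed SD differs from that under the within-sex SD (p = 10 / 30 / 50%):

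| Gains and SE | R = 2 | R = 3 |
|---|---|---|
| 1–8%, SE 0.015 | 23 / 52 / 62% | 49 / 92 / 94% |
| 1–15%, SE 0.015 | 11 / 26 / 31% | 25 / 49 / 52% |
| 1–8%, SE 0.03 | 11 / 20 / 21% | 20 / 34 / 38% |

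The first row looks alarming because most of its gains lie near a cut-point. A wider range of gains or a larger SE roughly halves the shares or cuts them further.

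**Direction of the alternative.** F is never below 1, so moving to the within-sex SD can only narrow the trivial zone. With R = 2, p = 50%, gains of 1–8% and SE 0.015, 44 of 71 labels change: 42 move up towards benefit, 2 become unclear, and none moves down the benefit scale.

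**The case for a change.** The best case for a change is that the mechanism is an identity, not a conjecture. In this SAP the labels are the conclusions. A mixed-sex SD can even turn an inconclusive result into one called clear, and a remedy would need only each subject's sex and a re-run. Sampling noise is no full defence either: random error in an SD does not excuse a systematic dependence on who enrolled.

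The mechanism stands, as does the possibility of a changed label if R is large. The step from there to a needed change is weaker:

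- The within-sex SD is another convention. It still depends on the age and body size of those recruited.
- The SAP is written in the past tense. Changing the yardstick on existing data, in a direction that mostly raises labels, would create a worse problem than the one it addresses.
- The reader is less in the dark than it seems. The SAP expresses effects in percent with 90% limits, and a reader who also has the baseline SD can rebuild the probabilities.
- The SAP does not itemise its basic anthropometric characteristics, so the absence of sex from the named variables is weak evidence that the sex mix will go unreported. Analysts routinely tabulate it.
- Adding sex as a covariate is a separate matter and does not touch the divisor. With 40 analysed it takes the error df from 37 to 36 (90% multiplier 1.687 to 1.688). If sex is unrelated to the change, the SE grows by about 1.4% on average. No gain has been shown to set against that.

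**Conclusion.** The observation is correct but conditional. If both sexes were analysed and differ at baseline, the 0.20 limit for lean mass, segmental lean mass and torque depends on the sex mix. So do the benefit and harm labels, if 0.20 is their limit. If one sex was analysed, the point disappears. Percent effects and their confidence limits are untouched either way.

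For R from 1 to 3, going from 10% to 50% of the minority sex moves the limit by 7% to 34%, and going from 30% to 50% moves it by 2% to 6%. The consequence ranges from negligible to a changed label, and the documents cannot place it within that range.

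No rule or figure in the plan is shown to be wrong. Standardising by the SD of the sample studied is a fair choice, and the alternative has its own drawback. The plan can stand. An author who wishes could report the sex mix, keep the SAP's labels as primary, and show labels under a pooled within-sex SD as a sensitivity analysis, noting that the smaller SD mostly strengthens labels.
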